## Introduction

***This study is designed to determine if Isomark's Canary infection monitor can provide an early indicator of the onset of infection.***

Healthcare-associated infections (HAIs) are the most common complication of hospital care, resulting in 1.7 million infections and 99,000 deaths each year. HAIs extend the average length of hospital stay by five times, costing the U.S. healthcare system more than \$35 billion each year (1). Serious HAIs that lead to extended hospital stays, and ultimately increased cost and risk of mortality, include blood stream infections, catheter-associated urinary tract infections, surgical site infections, and ventilator-associated pneumonia. These four infections account for more than 80 percent of all HAIs (2). Ventilator associated pneumonia, a common complication in mechanically ventilated patients, increases length of stay in the ICU by an average of six days, increases treatment costs by \$10,000 to \$40,000 per patient (3) and may result in a mortality rate greater than 30 percent (4).

Critically ill patients are at risk for infectious complications. Early detection of infections may lead to earlier treatment and reduce progression to systemic infectious processes like sepsis. Earlier diagnosis of sepsis and treatment as part of a resuscitation bundle has been shown to decrease sepsis related death rate in the critically ill (2). Localized infections that progress to sepsis and its more severe forms, severe sepsis and septic shock, have an unpredictable onset and progression. Sepsis is a leading cause of death in ICUs with mortality rates as high as 30% at some hospitals. Annually in the U.S., 1.4 million sepsis cases involve hospitalization, 750,000 cases of severe sepsis or septic shock, and ~260,000 cases of sepsis related death have been reported in recent years (1). Therefore, infection detection methods aimed at earlier diagnosis may result in earlier initiation of treatment and perhaps mitigate progression to sepsis and associated sequelae. However, the early detection of infection is a significant clinical challenge with diagnosis subject to clinician's clinical judgment and interpretation of overt infectious symptomology and laboratory profile. The healthcare system needs a better way to easily detect infections early and with confidence.

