Carbon-12 and carbon-13 are naturally abundant isotopes in expired breath carbon dioxide, can be measured accurately and have been demonstrated in proof-of-concept studies to be reliable indicators of the onset of severe infection. A change in the ratio of carbon-13 to carbon-12 (i.e.  $^{13}\text{CO}_2/^{12}\text{CO}_2$ ) in exhaled breath is known as the breath delta value (BDV). The ratio of  $^{13}\text{CO}_2/^{12}\text{CO}_2$  is expected to decrease, and produce a negative BDV trend, during severe stress such as infection. In animal models of sepsis, the BDV preceded other physiologic changes associated with infection (5, 6). In these preclinical studies, BDV was shown to be a possible early indicator of the onset of infection that precedes current, less direct indicators, such as changes in vital signs, mental status or white blood cell count.

Isomark, LLC (Madison, WI) has developed an investigational device, the Canary™ infection monitor which is intended to determine the BDV in critically ill patients. The Canary will be used in this study to determine the BDV of breath samples collected from patients who agree to participate as research subjects.

The objectives of this study are:

1. To measure variation of BDV with time in adult critically ill ICU patients who agree to participate as research subjects;
2. To determine the magnitude of change of BDV in subjects who are subsequently diagnosed with severe infection and/or sepsis;
3. To define variation of BDV in adult critically ill ICU subjects who do not develop severe infection.

In this multi-center study of 100 subjects, breath samples will be collected six times per day and research blood samples will be collected once per day. Analysis results of these research samples will be compared with data from subjects' medical records.

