### 5.2 ICU/IMC Days

This initial period of study days begins the day a subject is consented thru either discharge from the hospital or from an IMC/step-down unit to a general care status/unit. A study day will equal one calendar day. Day 1 will start at the time of the first breath collection and end at 23:59. Day 1 will typically be less than 24 hours and fewer than 6 breath samples may be collected. Research samples will be obtained until (1) the subject has been discharged to general care status/unit or (2) the subject has been discharged from hospital or (3) 28 days of breath sample collection has occurred, whichever comes first.

- Assess for capacity to consent (if subject did not previously provide consent)
- Research breath sample every 4 hours
  - Vital signs recorded concurrently
- Research blood draw once per calendar day
- Medical record abstraction

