## 5.5 Breath sample collection

Breath samples will be collected upon enrollment and every four hours thereafter until the subject is (1) discharged home or (2) to general care unit/status or (3) 28 days of breath sample collection has occurred, whichever comes first. Each sample should be collected in four-hour intervals, calculated from the initial sample time, with a window of  $\pm 1$  hour. The target time for sample collection will be determined when the first sample is collected and will not be reset if a subsequent sample is collected late or early. Samples collected outside of the specified time interval will still be analyzed. NOTE: Day 1 can start immediately after the baseline data collection is complete, and may occur on the same physical day. Therefore, it is likely that Day 1 won't have all 6 breath samples because of the shortened duration after the consent process.

Some subjects may be discharged from the study hospital in less than five days. If subjects are withdrawn (e.g. are discharged or died) on or before completing Day 5, they will be replaced in the overall enrollment numbers and not used in the primary analysis, though the data and breath samples collected will still be kept. Subjects who withdraw after completing Day 5, will have their data remain as part of the primary analysis. See Table 1 in section 5.12.

Breath sample collection bags will be provided by Isomark. Any unused bags will be returned to Isomark. Training documents about breath sample collection and storage are detailed in Isomark's Lab Manual. Collected samples will be labeled with site number, subject number, subject initials, date and time of collection. Collected samples will be stored in a secure location at the study hospital until sent to Isomark.

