### **7.2 Analysis plan**

Descriptive statistics will be generated. For continuous variables, descriptive statistics may include the number of subjects from whom data was used in the calculation, mean, standard deviation, median, minimum, and maximum; frequencies and percentages may be displayed for categorical data.

A 2-sample t-test will be used to compare the averaged (across time points) BDV between subjects who are diagnosed with an infection, without an infection, with sepsis and without sepsis. A linear mixed effects model with subject specific random effects will be used to compare BDV measurements between infected and non-infected and septic and non-septic subjects. This model will be also used to estimate the intra- and inter-subject variability of the BDV measurements. A paired t-test will be used to compare the BDV measurements prior to and after a diagnosis of infection or sepsis. Fisher's exact test and the Kappa statistic will be used to evaluate the relationship between a positive indication of infection by the BDV and a diagnosis of infection or sepsis in the subsequent 72 hours. Sensitivity, specificity, negative predictive value, positive predictive value and corresponding 95% confidence interval will be calculated.

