## **6. Analysis Sets/Populations/Subgroups**

The first task is to demonstrate that there is a positive signal associated with the Canary test using the subject as their own control.

A per protocol analysis will be performed following EAC event reconciliation and subsequent database lock. The EAC will determine diagnostic truth by documenting severe sepsis or septic shock events as well as the onset and resolution dates.

Infection documentation will be reviewed by the EAC committee based on best clinical practices, using four categories:

- No suspicion of infection
- Inconclusive evidence of infection
- High suspicion of infection
- Overt infection

For sensitivity and specificity, non-inferiority testing will be performed to rule out a -10% disadvantage according to a one-sided 97.5% lower confidence limit for the BDV – PCT

difference; exact McNemar paired comparison tests will be performed to test BDV non-inferiority relative to PCT. Both endpoints must achieve statistical significance in order to achieve study success.

PPV and NPV will be computed as observed and for a range of possible infection prevalence (10%, 20%, 30%, and 40%). Results will be analyzed in the same manner as sensitivity and specificity.

BDV variations will be assessed using a two-sample t-test to compare the averaged (across time points) BDV between subjects who are diagnosed with a severe sepsis and sepsis shock vs. no severe sepsis or sepsis shock. Also a linear mixed effects model with subject specific random effects will be used to compare BDV measurements between the two diagnostic groups. This model will be also used to estimate the intra- and inter-subject variability of the BDV measurements. A paired t-test will be used to compare the BDV measurements prior to and after a diagnosis of infection or sepsis.

The definition of a positive BDV will be based on a 72-hour window without advance knowledge of the diagnosis. In the absence of clinical details supporting PCT operating characteristics (sensitivity, specificity), two PCT thresholds (0.5 and 2.0) will be evaluated but the 0.5 threshold is deemed to be primary for BDV comparison.

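### The infected versus non-infected comparison of mean BDV names no common time window or study-day adjustment, so a BDV trend shared by both groups would bias it if infected subjects are monitored longer (cheap improvement)

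*Protocol*

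**What the plan says.** Protocol 7.2 gives two between-group analyses of BDV level. The first is a t-test: "A 2-sample t-test will be used to compare the averaged (across time points) BDV between subjects who are diagnosed with an infection" and those without one, and likewise for sepsis. The second is the mixed model: "A linear mixed effects model with subject specific random effects will be used to compare BDV measurements between infected and non-infected" subjects, and septic and non-septic subjects. SAP section 9 repeats both. SAP section 6 applies the same pair to severe sepsis or septic shock versus neither: "Also a linear mixed effects model with subject specific random effects will be used to compare BDV measurements between the two diagnostic groups". For the model, only the group comparison and the subject random effects are stated.

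The averaging window is set by each subject's stay. Under Protocol 5.2, sampling ends at discharge to general care, at hospital discharge, or when "28 days of breath sample collection has occurred, whichever comes first". Under Protocol 5.5, subjects withdrawn "on or before completing Day 5, they will be replaced in the overall enrollment numbers and not used in the primary analysis". Analysed windows therefore run from about 5 to 28 days.

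The Protocol Introduction expects stay to depend on infection. Ventilator-associated pneumonia "increases length of stay in the ICU by an average of six days", and, more broadly, "HAIs extend the average length of hospital stay by five times". The same section lists as its first objective "To measure variation of BDV with time in adult critically ill ICU patients", and SAP section 5 keeps a similar aim.

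**The concern.** If infected subjects are monitored longer, their averages contain more late study days. Any change in BDV over the stay that both groups share then enters the difference in averages. A random intercept does not remove it, because the intercept absorbs a subject's level and not the days on which that subject was observed.

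Both directions matter. A shared fall would resemble the hypothesised infection decrease. A shared rise, such as recovery from the admission insult, would mask a real decrease. Protocol 7.1 labels the mean BDV difference its primary hypothesis and sizes the study on it. How BDV moves over an ICU stay is one of the study's own open questions, so the plan should not depend on there being no trend.

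**Working it through.** **1. The plan's own power figures (Protocol 7.1).** Inputs: difference 2.0‰, SD 1.5‰, two-sided 5%. Standard error = SD × √(1/n₁ + 1/n₂).
- 5 versus 95: 1.5 × √(1/5 + 1/95) = 0.688‰, and 2.0/0.688 = 2.91. Noncentral-t power is 82.1%, against at least 80% stated.
- 10 versus 90: standard error 0.500‰, ratio 4.00, power 97.7%, against 98% stated.

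Both reproduce.

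**2. Closed form for the bias.** With a shared linear trend of b ‰/day, a subject monitored for L days has an average shifted by about bL/2. The false group difference is therefore b × (difference in mean monitored days)/2.

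Assumed stays: 5 days plus an exponential, capped at 28, with pre-cap means of 8 days (non-infected) and 14 days (infected). The six-day gap is the introduction's pneumonia figure; the 8-day mean is an assumption. After the cap the means are 8.0 and 13.3 days.
- b = 0.1: 0.1 × 5.3/2 = 0.27‰
- b = 0.2: 0.2 × 5.3/2 = 0.53‰
- A false difference of 2.0‰ at a full six-day gap needs 2.0/(6/2) = 0.67‰/day.

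**3. Simulation with no infection effect.** Six samples a day. Protocol inputs: inter-subject SD 1.5‰, intra-subject SD 1.16‰. SAP inputs: 1.0‰ and 0.95‰. Rejection rate of the t-test at nominal 5%:

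| Subjects (infected + not) | No drift | 0.1‰/day | 0.2‰/day |
|---|---|---|---|
| 5 + 95, Protocol SDs | 5% | about 6% | about 14% |
| 10 + 90, Protocol SDs | 5% | about 9% | about 19% |
| 97 + 97, SAP SDs | 4–5% | about 42% | about 90% |

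The last row is for scale only: the SAP sets 97 for its paired PCT comparisons, not for this t-test. At 0.05‰/day the rates on Protocol inputs are 5–7%.

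**4. Whether the mixed model helps.** With random intercepts and no day term, the bias equals that of the t-test (10 + 90 at 0.2‰/day: 0.517‰ versus 0.515‰). With a linear day term the bias is within ±0.03‰ and the error rate is 3.4–5.5%. When both groups have the same stay distribution, the bias is about 0 with or without the term.

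**5. Masking.** With 5 versus 95, a shared rise reduces the observable 2.0‰ to 1.73‰ at 0.1‰/day and to 1.47‰ at 0.2‰/day. Power falls from 82% to 70% and 56%.

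**6. A trend that fades.** A shared admission deviation of 1–2‰ fading over 5 days gives a false difference of about 0.1–0.2‰ and a t-test rate of about 5–8% on Protocol inputs.

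**The case against.** Several points on the other side stand.

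- **Silence is not exclusion.** A reader might infer that the mixed model leaves time out. The documents list no fixed effects beyond the group comparison, so they do not say whether time is included. The t-test on whole-stay averages, however, is fully specified and has no adjustment.
- **The drift is assumed.** No slope is given. SAP section 5 cites variability of about 0.5‰ in non-infected subjects with stable nutrition. Linear drift of 0.2‰/day over 10 days alone gives a within-subject SD of 0.2 × 10/√12 = 0.58‰, so sustained drift of that size sits uneasily with that figure, although its measurement period is not stated.
- **Not every trend does harm.** Bias needs durations that differ by group, and an early, fading trend does little.
- **The six-day gap is for ventilator-associated pneumonia.** Other infections may differ, and deaths (Protocol 9.2 expects about 35% mortality) can shorten monitoring.
- **Time is used elsewhere.** A reader might infer that no analysis involves time. In fact the paired before/after test, the 72-hour Fisher and Kappa analysis, and the lead-time and time-window work in Protocol 3.0 all do. None of them adjusts this between-group comparison.
- **The large error rates lie outside the success criterion.** A reader might take the 42% and 90% rates as a threat to the trial's conclusion. Under SAP sections 5 and 6, success rests on sensitivity and specificity against PCT.

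**Conclusion.** The point holds as a cheap improvement. The stated t-test compares averages over windows that the protocol itself expects to differ by group, and nothing stated for the mixed model corrects this.

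On Protocol inputs the effect is modest for drift of 0.1‰/day or less: a false difference of up to about 0.27‰ and an error rate of 5–9%. At 0.2‰/day it is material: about 0.53‰, with an error rate of 14–19%. It grows with the number of infected subjects. These sizes rest on an assumed linear slope shared by both groups, assumed stay distributions and a six-day gap. The documents do not support a claim that any trend becomes a false infection effect, nor that a false difference of the planned 2.0‰ is likely.

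The comparison is the sized primary hypothesis in the Protocol and a supportive analysis in the SAP.

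**What to change.** In Protocol 7.2 and SAP sections 6 and 9:

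1. State the mixed model's fixed effects and include study day, as categories or a spline.
2. Take the between-group contrast at the same study days from that model and name it as the between-group result.
3. Preferably let infection status vary with time from the adjudicated onset, so that pre-infection days do not count as infected. SAP section 6 already has the adjudication committee record onset and resolution dates for severe sepsis or septic shock; onset dates for other infections would need the same.
4. Label the whole-stay t-test as descriptive, or restrict it to study days matched between the groups.
5. Report the fitted day curve, which also serves the objective on BDV variation with time.

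The cost is a change of wording. Collection date and time are already recorded for every breath sample (Protocol 5.5 and 11.10). The day term uses a few degrees of freedom, and sparse late days will need pooling. It removes bias from a trend common to both groups; it does not correct for trends that differ between groups for reasons other than infection.

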## 2.0 Objectives

### 2.1 Primary objective

To define variation of BDV in critically ill adult subjects admitted to ICUs.

Hypothesis to be tested:

- Null hypothesis: BDV in critically ill adult ICU subjects is equal to BDV in non-infected adult ICU subjects.
- Alternative hypothesis: BDV in critically ill adult ICU subjects is different from BDV in non-infected adult ICU subjects.

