### 2.4 Specific aims

- To determine the positive and negative predictive value of  $^{13}\text{CO}_2/^{12}\text{CO}_2$  BDV determination as an indicator of infection in critically ill adult ICU subjects.
- To determine baseline variability of exhaled  $^{13}\text{CO}_2/^{12}\text{CO}_2$  BDV in a population of critically ill adult ICU subjects.
- To determine the response to treatment using the exhaled  $^{13}\text{CO}_2/^{12}\text{CO}_2$  BDV in a population of critically ill adult ICU subjects.

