### Hypotheses

#### Co-Primary Endpoint 1

1. Null hypothesis: BDV sensitivity is more than 10% worse than PCT sensitivity for progression to severe sepsis and septic shock in critically ill adult ICU subjects
2. Alternative hypothesis: BDV sensitivity is less than 10% worse than PCT sensitivity for progression to severe sepsis and septic shock in critically ill adult ICU subjects

#### Co-Primary Endpoint 2

1. Null hypothesis: BDV specificity is more than 10% worse than PCT specificity for those not progressing to severe sepsis and septic shock in critically ill adult ICU subjects
2. Alternative hypothesis: BDV specificity is less than 10% worse than PCT specificity for those not progressing to severe sepsis and septic shock in critically ill adult ICU subjects.

#### Secondary Endpoint 1

1. Null hypothesis: the variability of BDV in critically ill adult ICU subjects does not change after clinical diagnosis of progression to severe sepsis and septic shock.
2. Alternative hypothesis: the variability of BDV in critically ill adult ICU subjects increases after clinical diagnosis of progression to severe sepsis and septic shock.

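### Baseline BDV variability is estimated from a model that keeps readings taken during and after infection, so an infection-related drop inflates the intra-subject SD

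*Protocol*

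**What the plan says.** Two stated purposes concern BDV in the absence of infection. Protocol 2.4 has the aim "To determine baseline variability of exhaled" BDV in critically ill adults, and the Study Summary repeats it. The third objective in the protocol Introduction is "To define variation of BDV in adult critically ill ICU subjects who do not develop severe infection".

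The estimator is in Protocol 7.2. A linear mixed model with subject random effects "will be used to compare BDV measurements between infected and non-infected and septic and non-septic subjects". The next sentence gives the same model a second job: "This model will be also used to estimate the intra- and inter-subject variability of the BDV measurements". SAP section 6 assigns variability to the corresponding model for severe sepsis or septic shock, and SAP section 9 repeats the protocol text.

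Infection does not end sampling. Protocol 5.5 says "Breath samples will be collected upon enrollment and every four hours thereafter until the subject is" discharged home, moved to general care, or at 28 days. Table 1 in Protocol 5.12 keeps extra and out-of-window samples out of the primary analysis, but nothing is excluded because the subject was infected when the sample was taken.

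SAP section 5 (Hypotheses, Secondary Endpoint 1) expects that "the variability of BDV in critically ill adult ICU subjects increases after clinical diagnosis of progression to severe sepsis and septic shock".

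**The concern.** A term that labels a subject as infected or non-infected is constant over that subject's readings. With the random intercept it absorbs the difference in average level. It cannot absorb a fall that happens partway through the stay. If BDV drops at infection, as the study hypothesises, the before-and-after contrast within each infected subject is counted as residual variation, and the residual SD is what would be reported as intra-subject variability.

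That figure would then be too large for the baseline aim and for the objective about subjects without severe infection. A single pooled residual SD also sits badly with Secondary Endpoint 1, which expects the spread to change after diagnosis of progression.

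At stake is the accuracy of a reported result for a stated aim, and of anything later built on it, such as a limit set in SDs of baseline variation.

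**Working it through.** **The plan's own figures first.** Protocol 7.1 uses a difference of 2.0‰ and an assumed SD of 1.5‰.

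- 5 v 95, two-sided 5%: SE = 1.5 × √(1/5 + 1/95) = 0.688; 2.0/0.688 − 1.96 = 0.946; power 82.8% (82.1% by noncentral t). Stated: at least 80%.
- 10 v 90: SE = 1.5 × √(1/10 + 1/90) = 0.500; 4.00 − 1.96 = 2.04; power 97.9% (97.7% by noncentral t). Stated: 98%.
- Paired, one-sided 5%, noncentral t: n = 5 gives 78.7% (stated 79%); n = 10 gives 98.7% (stated 99%).

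These reproduce, and they rest on the assumed 1.5‰, not on the mixed model's output.

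**Inputs for the bias.**

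- Protocol 7.1: intra-subject SD s = 1.16‰; drop D = 2.0‰; share of subjects infected p = 5% or 10%; 18% is the top of the quoted 6 to 18% range.
- SAP section 5: s = 0.95‰; D = 1.0‰; p = 50%; also about 0.5‰ variability in subjects who do not develop infection.
- Not in the documents: f, the share of an infected subject's readings that follow the drop. I vary it over 0.10, 0.25 and 0.50. The term f(1 − f) is largest at 0.50 and symmetric, so 0.90 gives the same result as 0.10.
- Assumed: equal numbers of readings per subject, and s free of infection effects.

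**Formula.** Pooled within-subject SD = √(s² + p·f(1 − f)·D²).

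Example, protocol inputs at 5% and f = 0.5: √(1.3456 + 0.05 × 0.25 × 4) = √1.3956 = 1.181.

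| s, D (‰) | p | f = 0.10 | f = 0.25 | f = 0.50 | SD rise at f = 0.50 |
|---|---|---|---|---|---|
| 1.16, 2.0 | 5% | 1.168 | 1.176 | 1.181 | 1.8% |
| 1.16, 2.0 | 10% | 1.175 | 1.192 | 1.202 | 3.6% |
| 1.16, 2.0 | 18% | 1.188 | 1.217 | 1.235 | 6.5% |
| 0.95, 1.0 | 50% | 0.973 | 0.998 | 1.014 | 6.7% |
| 0.5, 1.0 | 50% | 0.543 | 0.586 | 0.612 | 22.5% |

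**Unequal stays.** If infected subjects contribute twice as many readings, replace p by w = 2p/(1 + p). At f = 0.5 and D = 2.0 the added variance is simply w. For p = 5%, w = 0.0952 and the SD is √(1.3456 + 0.0952) = 1.20. For 10% it is 1.24 and for 18% it is 1.28.

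**Simulation check** (100 subjects, 60 readings each, s = 1.16, D = 2.0, f = 0.5). Without a time-varying term the within-subject SD averaged 1.182, 1.204 and 1.233 at 5%, 10% and 18% infected. With a time-varying infection term it returned 1.157, 1.159 and 1.160. In one mixed-model fit at 10% infected, the within-subject SD was 1.207 with the group term only, 1.166 with a time-varying term, and 1.166 on pre-drop readings only.

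**The case against.** **The pooling is inferred from silence.** Section 7.2 does not say that the infection term is constant over time, and a paired t-test is listed for change around diagnosis. This stands as a caution about what would be programmed. But the text gives no restriction and no time-varying term, and the paired test compares levels, so it supplies no baseline SD.

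**A reader might infer that the primary objective is misestimated.** The documents do not support that. Section 2.1 reads "To define variation of BDV in critically ill adult subjects admitted to ICUs" and does not say baseline, so all-readings variation is not in itself wrong for it. SAP objective 4 concerns subjects who do not progress to severe sepsis or septic shock. That group can include infected subjects, whose infection readings would then belong in the estimate.

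**A reader might infer that cut-offs, power or pivotal sizing are affected.** They are not, as written. The 2.0‰ cut-off in Protocol 3.0 is fixed. The SAP's 1‰ comes from about 0.5‰ in subjects without infection. The pivotal-study parameters listed in Protocol 3.0 do not include this SD. A comparison of subject means would barely move: assuming 30 independent readings per subject, going from 1.16‰ to 1.24‰ adds about 0.18/30 = 0.006 to a variance of 1.5² = 2.25, or about 0.3%.

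**Larger figures are tempting.** Pairing the SAP's 0.95‰ and 50% with the protocol's 2.0‰ drop gives √(0.9025 + 0.5) = 1.18, a 55% rise in variance, but it mixes two sets of inputs. The Introduction's statement that "HAIs extend the average length of hospital stay by five times" concerns hospital stay in general, while sampling covers ICU/IMC time and stops at 28 days. If infection itself prolongs the stay, most readings follow the drop and f moves away from one half. At 5% infected and five-fold stays, w = 0.25/1.20 = 0.208; f = 0.5 gives 1.25, but f = 0.8 and 0.9 give 1.22 and 1.19.

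**The starting SDs may not be infection-free.** Both 1.16‰ and 0.95‰ are quoted irrespective of underlying condition. This stands: the table shows how the bias scales, not a forecast.

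**Cutting at onset is not enough.** The study looks for a fall before diagnosis, so readings just before onset may already contain it. This stands and shapes the fix.

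**Conclusion.** The point holds for the baseline-variability aim and for the objective on subjects without severe infection. As written, their only model-based estimator includes infection readings, and the intra-subject SD is biased upward if BDV drops as hypothesised.

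At the protocol's planned 5 to 10% infection rates the bias is small, at most about 2 to 4% of the SD. It is at most 6.5% at 18%. At the SAP's 50% rate and 1.0‰ change it is at most about 7% on 0.95‰ and about 22% on 0.5‰. These maxima assume equal readings per subject and half of the infected subject's readings after the drop. An earlier or later drop makes the bias smaller; more readings from infected subjects make it larger.

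The exposure is the reported baseline SD and later use of it. For illustration, a limit recomputed as 2 SD from 0.61‰ rather than 0.5‰ would be 1.22‰ instead of 1.0‰. No stated test, power figure or cut-off changes. The correction is worth making because the estimate would be wrong for a stated aim and the remedy is cheap.

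**What to change.** In Protocol 7.2 and SAP sections 6 and 9, choose one of two estimators for the baseline intra- and inter-subject SDs.

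1. Use non-infected subjects plus infected subjects' readings before infection, leaving out a pre-specified lead-in window before diagnosis or adjudicated onset. The 72 hours already used in Protocol 3.0 and 7.2 is one candidate. Since Protocol 3.0 defines the fall over 24 hours and looks for a diagnosis in the next 72, the authors should say whether the window also covers those 24 hours (24 + 72 = 96).
2. Keep all readings, but add a time-varying infection-state term with a separate residual variance after onset. The lead-in readings need a stated place in that term.

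Report the post-onset SD and the all-readings SD separately. Keep the all-readings model for the group comparison. The separate post-onset variance would also give Secondary Endpoint 1 a method that addresses spread; the listed t-tests compare means.

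Cost: a sentence or two in each document, one extra model, and no new samples. Somewhat fewer readings enter the baseline SD. An infection onset or diagnosis date must be used for each infected subject. Protocol 3.0 intends to determine onset timing, but Protocol 10.1 has the adjudication committee record infection status only, and SAP section 6 has it date severe sepsis and septic shock events. The plan should therefore name the source of the infection date.
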